3.0 STUDY POPULATION

3.1 SELECTION OF THE STUDY POPULATION

1. For Aims 1, 2 and 3A, data for patients will be obtained from the Cedars-Sinai electronic medical record.
2. For Aim 3B, a sample of 10 patients seen in the Hypertension Center or Women’s Heart Center clinic, who meet the pre-defined criteria for uncontrolled hypertension at the time of data procurement, will be selected.
3. For Aim 4A, a sample of 20 patients seen in the Hypertension Center or Women’s Heart Center as well as 7 medical providers will be selected to inclusion in interview discussions.
4. For Aim 4B, a sample of 60 patients hypertensive patients taking antihypertension medications will be selected.

3.2 INCLUSION CRITERIA

1. Patients seen at any Cedars-Sinai outpatient clinical (including OB/GYN) from 1/1/2012 through 3/30/2019.
2. Age >18 years at any time during the study period
3. Patients with blood pressure recordings in the EMR

4. At least 2 outpatient clinic visits in a 12-month period
5. Additional inclusion criteria for Aim 3B only:
 - Patients must be seen in the Hypertension Center
 - Patients must have a smartphone compatible with My CSLink, the Cedars-Sinai mobile health application (any smartphone running iOS or Android operating software)
6. Additional inclusion criteria for Aim 4A only:
 - Patients must be currently prescribed hypertension medication.
 - Providers and clinic staff must have been employed at clinic for 12 months.
7. Additional inclusion criteria for Aim 4B only:
 - Patients must be initiating or already taking antihypertension medication.

3.3 EXCLUSION CRITERIA

1. Patients only seen in inpatient, surgical, Emergency Department or Urgent Care settings
2. Patients with no blood pressure recordings in the EMR
3. Extra exclusion criteria for Aim 3B only:
 - Patient unwilling to sign up for My CSLink mobile health application
 - Inability to use a home blood pressure cuff
 - Patients only seen in OB/GYN settings
4. Additional exclusion criteria for Aim 4B only:
 - Patients not mentally fit to understand consenting procedures or do not own a cell phone

3.4 SUBJECT SCREENING AND ENROLLMENT

Subject screening applies only to Aim 3B, Aim 4A, and Aim 4B.

Aim 3B:

- a. Patients to be included in Aim 3B will be identified by physicians in the Hypertension Center, as part of his clinic panel.
- b. Eligible patients must have diagnosed hypertension but are not yet controlled (SBP<130 and DBP<80). Patients may already be on medications for hypertension.

Aim 4A:

- a. The research coordinator will monitor the clinic schedule for potentially eligible patients. The nurse manager of the clinic will be notified of the offer for physicians and nurses in the clinic to participate in interviews. Recruitment will occur for staff via institutional email.
- b. Eligible patients must currently be on hypertensive medication. Eligible staff must have been employed at the clinic for 12 months.

Aim 4B:

- a. The research coordinator will monitor the clinic schedule for potentially eligible patients together with clinic providers and staff. We will consent and enroll 1-2 patients/day during the 3-month recruitment period.
- b. Eligible patients must have hypertension and be initiating or already taking antihypertension medication.

3.5 SUBJECT RECRUITMENT

Subject recruitment applies only to Aim 3B, Aim 4A, and Aim 4B.

Aim 3B:

1. The Hypertension Center physicians will identify patients in his clinic who meet criteria for uncontrolled hypertension.
2. If the patient is agreeable, the clinical pharmacist will be contacted to complete enrollment. Enrollment will be completed during the same clinic visit at which the patient was identified, above. Informed consent will be obtained at that time. Further details of the enrollment process are detailed in Section 4.0, under ‘Intervention.’

Aim 4A:

1. The research coordinator will identify patients with hypertension that meet inclusion criteria via the clinic schedule. Clinic staff, including physicians and nurses, will be contacted via institutional email to offer participation in interviews. All emails will be internal and not used for contacting patients.
2. If the patient is agreeable, the research coordinator or physician will be contacted to complete enrollment. Enrollment will be completed during the same clinic visit at which the patient was identified, above. Informed consent will be obtained at that time.

Aim 4B:

1. The research coordinator will identify patients with hypertension initiating hypertension treatment via the clinic schedule.
2. All patients will receive written consent materials explaining the purpose and contents of the study. All interview members will also receive written consent materials explaining the purpose and contents of the study. We will explain clearly that participation in a specific intervention group is not a choice but based on random assignment (the Human Subjects Protection document elaborates on IRB-related issues). We will show all potential participants the MEMS device and explain its purpose. Each will receive \$50 USD for participation in each study assessment (baseline, month 1, month 2, month 3 and month 9).
3. Participants who are randomized into the incentive cohort and comply to greater than 80% medication adherence will be eligible to participate in a drawing every month for the first three months of intervention. The drawing will include a prize of either \$0, \$25, or \$50.
4. All participants will receive a parking validation.

Participants who are not consented during the clinic visit will have the option to telephone consent or to receive a unique link to an electronic REDCap consent form that then leads to a standardized REDCap e-Questionnaire (which will be administered electronically for the majority of participants but also accessible via mailed hard copy or telephone administration for participants with limited electronic access and/or expressed preference for a non-digital format).

4.0 STUDY DESIGN AND METHODS

Achieving these objectives and aims will involve an analysis of existing data from ambulatory care visits at clinics affiliated with Cedars-Sinai Medical Center from January 1, 2014 through March 30, 2019. Via a detailed study protocol, we will establish patient eligibility criteria, specify study variables and measures for extraction from the EMR, and specify descriptive and multivariate regression analyses

related to Aims 1-3. An Advisory Board consisting of local and national experts in EMR systems, population health, hypertension, and the implementation of quality improvement interventions will provide guidance and feedback on the protocol and after we have obtained preliminary data.

Patients will need to have at least two years of data available in CS-Link to be included in the study (defined as two or more clinic visits at least two years apart and occurring within the study dates). We will include ambulatory care visits with faculty, medical delivery network, and private physicians in all specialties if they use CS-Link. We will exclude care in the emergency department, urgent care, and hospital settings because blood pressure may be temporarily elevated due to acute illness. For eligible visits, we will obtain the recorded blood pressure values, whether the blood pressure was assessed manually or automatically (if available), and the physician identity (coded).

We will define blood pressure control based on the 2017 ACC/AHA guidelines (blood pressure <130/80). In sensitivity analyses, we will also consider control based on the JNC-7 guidelines (blood pressure <140/90), due to the recent change in the standard of care.

We will create three time-to-care measures: time-to-diagnosis, for patients who qualify for new diagnoses; time-to-initiate, for the same patients; and time-to-intensify, for patients with established diagnoses. We will create two time-to-control measures, one for patients with new and one for patients with established diagnoses. The new time-to-care and time-to-control measures will be based on the 2017 ACC/AHA guidelines. We will define undiagnosed hypertension as two ambulatory blood pressures \geq 130/80 without an ICD-9/10 code for hypertension in the preceding year; uncontrolled hypertension will be defined using the same blood pressure criterion but patients will have an ICD-9/10 code for hypertension. A new diagnosis of hypertension will be defined as an ICD-9/10 code for hypertension without a prior code or antihypertensive medication use in the preceding year. We will define treatment initiation as the first prescription for an antihypertensive medication following a new diagnosis of hypertension. Treatment intensification will represent the addition of another antihypertensive medication, an increase in the dose of an existing antihypertensive medication, and a change from one antihypertensive medication to another. We will access the 2017 guidelines and other standard sources to develop a list of antihypertensive medications. Time to care will be calculated as the number of days from the last blood pressure above goal to the documentation of the diagnosis or the initiation/intensification of treatment. Time to control will be calculated as the number of days from the last blood pressure above goal to the first blood pressure at goal.

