
Research Procedures
	
 • The primary research procedures for Aims 1, 2 and 3A are a retrospective review of blood pressure levels for outpatients in the Cedars-Sinai system before and after the introduction of the new clinical guidelines. • Aim 3B is a pilot study to assess the use of home blood pressure monitoring linked to the electronic medical record. This is a prospective intervention of an already approved device, which is compatible with the Cedars-Sinai electronic medical record system and promoted on the Cedars-Sinai website. Study participants for this feasibility study will only include patients already under the care of the PI. • Aim 4A involves conducting interviews discussions to understand the feasibility and implementation of an intervention to increase medication adherence. Participants in the interviews will include current patients who are taking hypertension medications as well as clinic staff. • Aim 4B is a pilot study to evaluate the feasibility, acceptability, and efficacy of an intervention to increase medication adherence involving text message reminders and small incentives for adherence to pill-taking routines.

Subject Population
	
 • For Aims 1-3: All patients seen at least twice in a 12-month period at any Cedars-Sinai outpatient facility • For Aim 4A: All patients with hypertension currently taking hypertension medication and clinic staff • For Aim 4B: All patients with hypertension taking hypertension medication

Duration	
 • For Aims 1, 2 and 3A, all data is retrospective, using already available data collected during routine care. The data to be utilized was collected as part of clinical care from 1/1/2012 through 3/30/2019. • For Aim 3B, prospective data collection will occur during a 9 week period, beginning at the time of patient enrollment. • For Aim 4A, interviews will last one hour on regular clinic days. • For Aim 4B, prospective data collection will occur during a 9 month period, beginning at the time of patient enrollment.
----------	--

GENERAL INFORMATION

CSMC Co-Investigators	
[name], MS [name]
 
[name] [name]

Sponsor/Funder	NIH/NHLBI
Collaborating Institutions Involved in the Research	
RAND Corporation [name]

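### Aims 1–3A carry two start dates and two unreconciled entry rules; where the two-years-apart rule applies, entry closes on 30 March 2017 and case mix drifts across the Aim 3A time series

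*Protocol*

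**What the plan says.** **Window.** The Duration row of the protocol's front summary table says of Aims 1, 2 and 3A: "The data to be utilized was collected as part of clinical care from 1/1/2012 through 3/30/2019". Section 3.2 agrees ("Patients seen at any Cedars-Sinai outpatient clinical (including OB/GYN) from 1/1/2012 through 3/30/2019"), and section 5.2 repeats the 2012 start. Section 4.0 instead analyses visits "from January 1, 2014 through March 30, 2019".

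**Entry rule.** For Aims 1–3 the Subject Population row admits "All patients seen at least twice in a 12-month period at any Cedars-Sinai outpatient facility", and section 3.2 lists "At least 2 outpatient clinic visits in a 12-month period". Section 4.0 makes two years of data in CS-Link a condition of inclusion, defined as "two or more clinic visits at least two years apart and occurring within the study dates".

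**Provisional wording.** Section 4.0 also says "Via a detailed study protocol, we will establish patient eligibility criteria". Section 7.1 lets Aim 2 refine the measures step by step, including by excluding readings, visit types or patient groups. Neither passage chooses a window or an entry rule.

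**Use.** For Aim 3A, section 7.1 plans interrupted time-series models by quarter for time-to-care, time-to-control and control rates. They look for a shift in level or trend in any quarter after the 2017 guideline announcement. The adjustment variables in section 4.0 are patient demographics, payer, comorbidities, and physician and clinic characteristics. Time since first visit is not among them, although Table 1 (section 5.4) collects the date of every clinic visit.

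**The concern.** Two analysts following this protocol could build different cohorts: 29 or 21 quarters, with or without a two-year retention requirement.

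The two-year rule matters beyond tidiness because it selects on attendance far from the reading being analysed. Aim 3A compares quarters. If the kind of patient in a quarter changes over the series, a change in measured performance may reflect who is included and not how clinicians responded to the guideline. Newly seen patients matter here: three of the five measures (time-to-diagnosis, time-to-initiate and one of the two time-to-control measures) concern new diagnoses. The second Aim 3A hypothesis also depends on some measures staying stable while others worsen, so a compositional trend could imitate that pattern or hide it.

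For Aim 1, prevalence estimated under the two-year rule would describe patients who stayed in the system for two years, not the population named in the summary table.

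**Working it through.** **1. The plan's own volume figure.** Section 7.2 expects over 500,000 visits a year and over 2.5 million readings in the study period. Assuming one reading per visit, 2,500,000 / 500,000 = 5.0 years.
- 2014 start: 5.24 years × 500,000 = 2.62 million.
- 2012 start: 7.24 years × 500,000 = 3.62 million.

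The stated figure is closer to the 2014 start. It is a floor, so it does not exclude 2012.

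**2. Number of quarters.** 2012 Q1 to 2019 Q1: 7 × 4 + 1 = 29. 2014 Q1 to 2019 Q1: 5 × 4 + 1 = 21.

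**3. Closing date under the two-year rule.** 30 March 2019 minus two years = 30 March 2017. This is the latest first in-window visit that can qualify, whichever start date holds and whether or not the 12-month rule applies as well.

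**4. Quarters with no newly seen patient.** 2017 Q2 to 2019 Q1 is 8 quarters: 8/29 = 27.6% or 8/21 = 38.1%. The documents do not give the quarter of the 2017 announcement. If it fell in Q1, Q2, Q3 or Q4, then 8, 7, 6 or 5 quarters follow it, and all of them lie within these 8.

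**5. How the selection changes.** A patient seen in the first two years of the window qualifies only by attending later. A patient seen in the last eight quarters must have been first seen by 30 March 2017. Everyone included has therefore been known for at least 9 months at the start of 2018 and at least 21 months at the start of 2019.

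**6. Thinning before the closing date (illustrative only).** Assume visits at random at rate r per year and no departures. The chance that a newly seen patient qualifies is 1 − exp(−r × T), averaged over the days of the quarter, where T is the time from two years after the first visit to 30 March 2019. Mean T is 13.5 months for 2016 Q1 and 1.5 months for 2017 Q1.

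| r per year | 2016 Q1 | 2017 Q1 | 2017 Q2 on |
|---|---|---|---|
| 1 | about 67% | 11–12% | 0 |
| 2 | 89% | 21% | 0 |
| 6.67 (500,000/75,000) | almost 100% | 50% | 0 |

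These are not bounds. Two visits in one 12-month period does not mean two visits every year, so the documents give no lower limit for r. Departures would lower every figure.

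**7. Comparing the two rules (illustrative simulation).** Assumptions not in the documents: constant arrivals, exponential time in the system with mean 2, 4 or 8 years, and 2 or 4 visits a year. With a 2014 start, the share of retained visits made by patients in their first year in the system was:
- two-year rule: 15–51% in 2014 Q1, 3–11% in 2017 Q3, about 0.2–1% in 2018 Q1, and 0 from 2018 Q3;
- 12-month rule: 15–52% in 2014 Q1 and 14–46% in 2018 Q4.

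The 12-month rule also looks forward, but only by up to 12 months, and it produced little drift.

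**The case against.** **The entry rules can coexist.** A patient can satisfy both, so only the start dates contradict each other outright. That stands. But the summary table says all patients meeting the 12-month rule, section 3.2 omits the two-year rule, and no passage says the two are cumulative. If they are, the two-year rule still binds and the closing date is unchanged.

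**Eligibility is provisional.** Section 4.0 defers to a detailed protocol, and section 7.1 allows later exclusions. That lowers the stakes, but section 4.0 then states a definite, mandatory rule, and neither provision addresses the selection.

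**There is no step at the break.** If the announcement came in Q2 to Q4 of 2017, entry had already closed by the end of that quarter, and in the simulation most of the fall in first-year patients came before 2017 Q3. This also stands. A reader might infer that the rule creates a false guideline effect; the documents support only a gradual drift over the same period, with unknown effect.

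**The late quarters are not empty.** A reader might infer that new diagnoses disappear after March 2017. They need not: a patient already known to the system can still receive a first code.

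**The measures have their own look-back.** Undiagnosed hypertension is defined "without an ICD-9/10 code for hypertension in the preceding year". That does not standardise observation time, because a year with no recorded visits also contains no code.

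**This is pilot work.** Aims 1–3A support a grant application, and changes are to be compared across measures qualitatively. That argues for a modest grading, not for leaving the text unreconciled.

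**Conclusion.** The point holds as a conditional one. The start-date conflict (29 against 21 quarters) is plain on the page, and the relation between the two entry rules is unstated. Wherever the two-year rule applies, the last 8 quarters, including all 5 to 8 after a 2017 announcement, contain no patient first seen in them. Case mix therefore moves gradually towards longer-known patients, and nothing in the adjustment list accounts for it. This part rests on date arithmetic alone.

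What cannot be concluded is that the Aim 3A results would be biased by any given amount or in any given direction. The thinning and simulation figures describe who enters, not bias, and rest on assumed visit and departure patterns. The randomised Aim 4B comparison is not touched. The matter should be settled before the EMR query is run.

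**What to change.** 1. **One window.** State the same start date in the summary table and sections 3.2, 4.0 and 5.2. If 2012–2013 is meant only as look-back data for a 2014 analysis start, say so.
2. **Entry from past visits.** For Aim 1 and the Aim 3A time series, do not condition entry on the two-years-apart rule. Define eligibility from visits before the index reading or quarter, for example two visits in the preceding 12 months, applied from the first quarter with a full look-back. Report the two-year cohort as a sensitivity analysis. If the sponsor prefers the two-year rule as primary, say whether the 12-month rule applies too, report the series without the two-year rule as the sensitivity analysis, and state the limitation.
3. **Time since first visit.** Adjust for, or stratify the series by, time since first in-window visit (under 12 months, 12 months or more), derived from the visit dates in Table 1. This alone does not rescue the two-year cohort: its under-12-months group is empty after 30 March 2018 (30 March 2017 plus 12 months).

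**Cost.** Protocol wording, a changed EMR query and one derived variable. Late entrants have shorter follow-up. The first four quarters are lost for want of a full look-back (29 − 4 = 25 or 21 − 4 = 17 remain), unless data are pulled from 2012 and analysed from 2014, when all 21 are kept. Every post-announcement quarter is kept in each case.

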prevalence of undiagnosed and uncontrolled hypertension at Cedars-Sinai is high, slow uptake of these new standards may be one explanation. However, another potential explanation is the much greater level of effort needed to attain the lower blood pressure goals. If clinicians are recognizing uncontrolled hypertension and initiating or intensifying treatment, we would expect the time-to-care measures to exhibit stable performance after 2017 while performance on the time-to-control measures and cross-sectional control rates would decline.

We will also examine how performance on the time-to-care and time-to-control measures varies based on the setting in which blood pressure is measured. If we find that that performance on these time-to-care and time-to-control measures as well as control rates are better in Primary Care, Internal Medicine, Nephrology, or Cardiology clinics than in other specialty and subspecialty clinics, this would suggest the EMR may be a useful for the screening and detection of patient populations that would benefit from efforts to make a diagnosis and initiate or intensify treatment.

Aim 3B – We will perform a pilot study of the new time-to-control measure’s responsiveness to more intensive blood pressure monitoring and intervention. This pilot will provide a subset of uncontrolled hypertensive patients with home blood pressure monitors linked to the EMR at Cedars-Sinai. This information will be monitored and acted upon weekly, allowing for a more rapid titration of medical therapy. A decrease in the time-to-control measure of blood pressure management would be a preliminary finding consistent with measure responsiveness.

Aims 4A and 4B: Aim 4A – We will conduct interview discussions to explore feasibility and acceptability of text message reminder and incentives for blood pressure medication adherence. These interview discussions will involve both patients and providers and will allow for a better understanding of existing routine behaviors that support pill-taking, appropriate messaging for text message reminders, and how to best implement the intervention.

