7.0 STATISTICAL CONSIDERATIONS

7.1 STUDY OUTCOME MEASURES

Analyses will test the following pre-specified hypotheses for each goal:

Aim	Hypotheses
1: Determine cross-sectional prevalence of undiagnosed and uncontrolled hypertension at CSMC, as well as the patient, physician, and clinic characteristics associated with these outcomes.	
 1) Cross-sectional rates of undiagnosed and uncontrolled hypertension at CSMC, based on the 2017 AA/AHA Guidelines, will be similar to national rates (20% and 50%, respectively). 2) Cross-sectional rates of undiagnosed and uncontrolled hypertension will be higher under the 2017 ACC/AHA Guidelines than the JNC-7 Guidelines. 3) Rates of undiagnosed and uncontrolled hypertension will be lower among patients with visits in Primary Care, Internal Medicine, Nephrology, or Cardiology clinics than for patients who only receive care in other clinics.
2: Develop and pilot test new time-to-care and time-to-control measures.	
 1) Data already collected in the EMR can be used to calculate these five new measures of hypertension care.
3A: Assess the validity, responsiveness, and potential utility of the new time-to-care and time-to-control measures.	
 1) Performance on the time-to-care and time-to-control measures will be associated with cross-sectional control rates at the clinic and physician level. 2) Following release of the 2017 ACC/AHA Hypertension Guidelines, performance on the time-to-control measures and cross-sectional control rates will worsen while performance on time-to-care measures will remain stable. 3) Performance on the time-to-care and time-to-control measures will be better for patients with visits in Primary Care, Internal Medicine, Nephrology, and Cardiology clinics than for patients who only receive care in other clinics.

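### Aim 3A tests the 2017 guideline change against one fixed <130/80 goal, so the lower goal cannot itself produce the predicted worsening, and the reading of hypothesis 2 as clinicians responding is inverted

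*Protocol*

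**What the plan says.** Protocol section 4.0 sets the threshold for control: "We will define blood pressure control based on the 2017 ACC/AHA guidelines (blood pressure <130/80". For the other measures it says "The new time-to-care and time-to-control measures will be based on the 2017 ACC/AHA guidelines", and it places both undiagnosed and uncontrolled hypertension at 130/80 or above. The clock is defined as follows: "Time to control will be calculated as the number of days from the last blood pressure above goal to the first blood pressure at goal".

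The records run "from January 1, 2014 through March 30, 2019" in section 4.0, and from 2012 in sections 3.2 and 5.2. Either window spans the 2017 release. No section makes the goal depend on the visit date. The one alternative is also a single fixed value, and it is written for control only: "In sensitivity analyses, we will also consider control based on the JNC-7 guidelines (blood pressure <140/90), due to the recent change in the standard of" (the quote stops one word short of the end of the sentence).

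Aim 3A hypothesis 2 (section 7.1) predicts that after the release "performance on the time-to-control measures and cross-sectional control rates will worsen while performance on time-to-care measures will remain stable". Section 2.0 gives the reason: "the much greater level of effort needed to attain the lower blood pressure goals". It adds that this pattern is what one would see if clinicians were recognising and treating uncontrolled hypertension. Section 7.1 tests the hypothesis with an interrupted time series by quarter, looking for a shift in level or trend after the release. The same paragraph expects time-to-care to prove the more responsive measure.

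**The concern.** The stated mechanism needs the goal to fall at the interruption, and in the measures as defined it does not. A patient at 134 mmHg counts as uncontrolled in 2015 and in 2018 alike. What can change in 2018 is that a clinician now acts on that reading.

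The protocol would therefore read its own results the wrong way round. Flat time-to-care, which a fixed goal gives when practice does not change, would be taken as clinicians responding. Shorter time-to-care with better control, which uptake would be expected to give, would count against hypothesis 2. Aim 3A uses this comparison to judge whether the new measures respond to changes in practice, so a wrong expected direction could lead to a wrong judgement of the measures.

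**Working it through.** The documents give no effect size, SD, alpha or power for Aim 3A, so there is no figure to reproduce. The check concerns direction; the sizes are illustrations.

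**Step 1. Predictions side by side, goal fixed at 130/80.**

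| Practice after 2017 | Time-to-care | Control and time-to-control | Hypothesis 2 |
|---|---|---|---|
| Uptake: clinicians act on readings of 130–139 | shorter | stable or better | stable; worse |
| No uptake | no change | no change | stable; worse |

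No uptake matches the time-to-care half of the hypothesis. Full uptake matches neither half, unless control merely fails to improve.

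**Step 2. Control rate.** Inputs: section 1.0 says half of hypertensive individuals exceed <130/80, so mean systolic pressure before release is set at 130. Assumptions: normal distribution, systolic only, SD 15 (range 12–20), fall in the mean after release of 0–5 mmHg.

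Formula: control = Φ((goal − mean)/SD).

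- Fixed <130, no fall: Φ(0/15) = 50.0% before and after.
- Fixed <130, 3 mmHg fall: Φ(3/15) = 57.9%, or +7.9 points.
- Fixed <130, 5 mmHg fall: Φ(5/15) = 63.1%, or +13.1 points.
- Fixed <130, SD 12–20, falls of 3–5 mmHg: +6.0 to +16.2 points.
- Fixed <140, same range: +5.1 to +9.7 points.

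Neither fixed goal gives a decline when pressures fall, and neither moves when pressures do not.

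**Step 3. What a goal that switches at release would do.** With <140 before and <130 after, SD 15:

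- No change in any pressure: Φ(10/15) = 74.8% to 50.0%, or −24.8 points.
- 3 mmHg improvement: 74.8% to 57.9%, or −16.8 points from unrounded values.
- SD 12–20, falls of 0–5 mmHg: −9.3 to −29.8 points.

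The predicted worsening appears in every scenario, including those where pressure improves. That step comes from the definition.

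**Step 4. Time measures.** One toy simulation, all inputs assumed: starting systolic mean 145, SD 12; visit noise SD 8; 40% chance of a 5 mmHg reduction at a visit above the clinician's target; 24 visits. With the measure fixed at 130 and clinicians moving from a 140 to a 130 target, mean time-to-care goes from 5.00 to 2.05 visits and time-to-control from 7.76 to 6.51. With the measured goal also switching from 140 to 130, time-to-control goes from 3.75 to 6.51 visits and time-to-care from 3.31 to 2.05, so even then time-to-care is not stable.

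The simulated clock starts at the first above-goal reading, not the last as section 4.0 has it. Read literally, the protocol's time-to-control is close to the gap between two visits and may respond little to any goal.

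**Step 5. Case mix.** Suppose the denominator is patients coded as hypertensive. Start with 100 patients at 50% control, then add m newly coded patients of whom a fraction c are controlled: control = (100p + mc)/(100 + m), with p the control rate in the original 100.

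- p = 0.50, m = 30, c = 0: 50/130 = 38.5%.
- p = 0.50, any m, c = 0.5: 50.0%.
- p = 0.58, m = 30, c = 0: 58/130 = 44.6%.
- p = 0.58, m = 10, c = 0.5: 63/110 = 57.3%.

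Fixed-goal control can therefore fall after release, but through who is counted.

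**The case against.** The strongest reply is that worsening is not ruled out. A reader might infer from the fixed goal that no decline can appear at all; the documents do not support that. Section 2.0 says the guideline changed the criteria for diagnosis as well as the goals, and section 4.0 requires a diagnosis code for uncontrolled hypertension. More coding after 2017 could pull control down, as step 5 shows. The Aim 1 text in section 7.1 speaks of all patients with ambulatory visits, while the 50% benchmark in section 1.0 refers to hypertensive individuals, so the denominator is not settled. This stands, and it limits the point to worsening caused by the lower goal itself.

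Second, the time-series paragraph names no threshold, so the fixed goal is carried over from section 4.0. That is true, but section 4.0 is the only definition given. The refinement foreseen under Aim 2 concerns excluding readings, visits or populations, not a threshold that depends on date.

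Third, a reader might infer that the JNC-7 sensitivity analysis is of no use here. That goes too far. If produced by quarter, it supplies the pre-release half of a goal-in-force control series. It does not restore the mechanism, because it is fixed too, and it does not cover the time measures.

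Fourth, a constant definition is the defensible choice for measuring a change in practice, and a test that can contradict its hypothesis is doing its job. This also stands. The fault lies in the predicted directions and their interpretation, not in the fixed goal.

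**Conclusion.** The point holds in this form: with one <130/80 goal throughout, the lower goal cannot itself produce the worsening that hypothesis 2 predicts, and reading stable time-to-care with worse control as clinicians responding is inverted. It follows from sections 2.0, 4.0 and 7.1 read together. The expected direction under uptake also assumes that acting on readings of 130–139 lowers pressure or at least does not raise it.

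The sizes are illustrative: +6.0 to +16.2 points in fixed-goal control for a 3–5 mmHg fall, systolic only, with assumed mean and SD. The time-measure figures come from a single toy model.

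A reader might infer that the goal should switch at release and that series be tested. The protocol does not call for this, and step 3 shows that it would confirm the control part of hypothesis 2 by construction.

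The matter is confined to Aim 3A. The Aim 4B randomised pilot and the SAP are not touched.

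**What to change.** 1. Keep the fixed-130/80 interrupted time series as the test of responsiveness.
2. Restate hypothesis 2 in section 7.1 and its interpretation in section 2.0 for that series. Uptake: time-to-care shorter, control and time-to-control stable or better. No uptake: no change.
3. Reconcile the two statements in section 7.1, one expecting time-to-care to stay stable and the other expecting it to be the more responsive measure.
4. State the denominator of the control rate and hold its definition constant across the release, or report results with and without newly coded patients.
5. Run the fixed <140/90 version for the time measures as well as for control.
6. If a goal-in-force series is shown, label it descriptive. Its step at release is definitional and should not be tested as a change in care.

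The cost is a few sentences, one more threshold for the time measures and one denominator comparison, all from data already being extracted. The downside is a hypothesis whose predicted direction changes, so the restatement should be recorded before the quarterly series are examined.
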